Effect on cervical mucus score	Mucus score at V2 R - score at V2 R-1 (Day 41±3): change from baseline to 3 (delayed pill period) or 6 hour (missed pill period) after infringement	Repeated measures mixed model	14.2.1
	Mucus score at V2 R+1 - score at V2 R-1 (Day 41±3): Change from baseline to just before pill intake the day after infringement	Repeated measures mixed model	14.2.1
	Mucus score at V3 R - score at V3 R-1 (Day 69±3): Change from baseline to 3 (delayed pill period) or 6 hour (missed pill period) after infringement	Repeated measures mixed model	14.2.1
	Score at V3 R+1 - score at V3 R-1 (Day 69±3): Change from baseline to just before pill intake the day after infringement	Repeated measures mixed model	14.2.1
Duration of the protective effect of cervical mucus	Full protection by cervical mucus regardless of the use of norgestrel 75 mcg	McNemar	14.2.3
	Absence of risk increase further to delayed intake	McNemar	14.2.3

Efficacy Objective	Efficacy Endpoint	Statistical Test	Table Number
	Absence of risk increase further to missed pill	McNemar	14.2.3
	Absence of risk increase due to infringement regardless of the type	McNemar	14.2.3
	Transient risk increase further to delayed intake	McNemar	14.2.3
	Transient risk increase further to missed pill	McNemar	14.2.3
	Prolonged risk increase further to delayed intake	McNemar	14.2.3
	Prolonged risk increase further to missed pill	McNemar	14.2.3
Percentage of subjects with a protective cervical mucus score	The percentage of subjects with cervical mucus score $\leq 4$ , between 5 and 8 (inclusive), and $\geq 9$ in reported perfect use period	McNemar	14.2.6
	The percentage of subjects with cervical mucus score $\leq 4$ , between 5 and 8 (inclusive), and $\geq 9$ in delayed pill intake periods	McNemar	14.2.6
	The percentage of subjects with cervical mucus score $\leq 4$ , between 5 and 8 (inclusive), and $\geq 9$ in missed pill periods	McNemar	14.2.6
	The percentage of subjects with cervical mucus score $\leq 4$ in all periods	McNemar	14.2.6
Ovarian activity	The percentage of subjects with $OS_q$ , $OS_a$ , $OS_{alp}$ and $OS_{nlp}$ in reported perfect use period	McNemar	14.2.9
	The percentage of subjects with $OS_q$ , $OS_a$ , $OS_{alp}$ and $OS_{nlp}$ in delayed pill intake periods	McNemar	14.2.9

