## 2.5 Sample Size Consideration

Approximately 70 subjects will be screened to have at least 45 subjects who complete the study.

The primary analysis is based on the score of cervical mucus as a quantitative variable because it is expected to be the most powerful analysis based on the consistent mechanism of action of norgestrel on cervical mucus. However the justification of the sample size will not be based on the primary analysis as there is no basis provided by published data on this parameter, such as order of magnitude of the variance covariance matrix of the change from time point of reference. This is the reason why the sample size calculation will be based on proportions of women with no loss of protection.

A total sample size of 45 subjects who complete the study should allow to detect a loss of protection that would demonstrate a pertinent effect on a substantial proportion of the population. Indeed if the difference between a cycle (or day) with a perfect use and a cycle (or day) with an infringement in the schedule is 14 % in the expected proportions of women with a loss of protection at any time and if the proportion of discordances between the 2 situations is 17% then the exact power is equal to 79.1%. If the expected difference in proportions is 15% with a rate of discordance of 18% then the exact power is 82.4% for an unconditional test. The expected difference in proportions need, therefore, to reach 14-15 % to get a sufficient power for detecting a significant difference. This difference in proportions is a substantial difference knowing that most of change in status are in the same direction i.e. from protection to loss of protection.

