Comparison between the missed pill and the delayed pill can easily be performed and tested through a stratified McNemar test (stratification on the site, CMH option in SAS). The SAS glimmix procedure for repeated measures was not retained for decision making test because convergence issues in fitting the model are too frequent. The first null hypothesis is  $H_0$ : Proportion of protected women at baseline (R-1) is equal to the proportion of protected women after schedule infringement and more specifically at Day R (27 hours and 30 hours post treatment). The second null hypothesis (which is only performed for the missed pill arm) is the equality of proportions at baseline (R-1) and at Day R+1 (48 hours post treatment).

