### 3.7.2 Secondary Efficacy Analyses

#### 3.7.2.1 Cervical mucus protection in each type of treatment period

The aim of this secondary objective is to assess the level of cervical mucus protection during reported perfect use, during a treatment period with a delayed pill intake of 6 hours and during a treatment period with a missed pill of norgestrel 75 mcg. The FASM population will be used for the analysis and a sensitivity analysis will be done using ITT and PP.

The time frames are:

- reported perfect use: all the visits of the period 1
- delayed pill intake: all the visits of the period 2 for Arm A and all the visits of period 3 for Arm B.
- missed pill: all the visits of the period 2 for Arm B and all the visits of period 3 for Arm A.

The assessment criterion is the cervical mucus score. The cut off is a cervical mucus score of 4. There is conception protection by cervical mucus if the cervical mucus score is  $\leq 4$ .

The endpoints are:

- The percentage of subjects with cervical mucus score  $\leq 4$ , between 5 and 8, and  $\geq 9$  in reported perfect use period
- The percentage of subjects with cervical mucus score  $\leq 4$ , between 5 and 8, and  $\geq 9$  in delayed pill intake periods
- The percentage of subjects with cervical mucus score  $\leq 4$ , between 5 and 8, and  $\geq 9$  in missed pill periods
- The percentage of subjects with cervical mucus score  $\leq 4$  in all periods

If the cervical mucus was too thick to be collected (and thus a cervical mucus score could not be obtained) the analysis will consider the sample to have good contraception protection and have a cervical mucus score  $\leq 4$ . Otherwise if the cervical mucus score is missing the subject will not be included in the analysis. A period must have at least 7 cervical mucus assessment to be included in the summaries. A stratified McNemar test (stratification on the site, CMH option in SAS) will be used to compare the distribution of cervical mucus scores in the perfect use period to the delayed and missed pill periods (pairwise vs perfect use).

The worst (meaning highest) cervical mucus score in the period will be used for the analyses.

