### 3.7.2.2 Ovarian activity in each type of treatment period

The aim of this secondary objective is to describe the distribution of the ovarian status among the subjects, during reported perfect use, during a treatment period with a delayed pill intake of 6 hours and during a treatment period with a missed pill of norgestrel 75 mcg. The adjudication committee will evaluate whether cycles should be excluded from analyses (including period 1 cycles if low compliance of taking study drug). The details for the review process will be defined in a separate document prepared for the adjudication process. The FASO population will be used for the analysis and a sensitivity analysis will be done using ITT and PP.

The time frames are:

- reported perfect use period: all the visits of the period 1
- delayed pill intake period: all the visits of the period 2 for Arm A and all the visits of period 3 for Arm B
- missed pill period: all the visits of the period 2 for Arm B and all the visits of period 3 for Arm A

The assessment criterion is the OS as defined in Appendix 5.4.

The OS are ranked depending on the risk of conception:  $OS_{nlp} > OS_{alp} > OS_a > OS_q$ . The OS classification will be determined by the adjudication committee.

For each treatment period the most risky OS will be considered.

The endpoints are:

- The percentage of subjects with  $OS_q$ ,  $OS_a$ ,  $OS_a/OS_{alp}$  and  $OS_{nlp}$  in reported perfect use period
- The percentage of subjects with  $OS_q$ ,  $OS_a$ ,  $OS_a/OS_{alp}$  and  $OS_{nlp}$  in delayed pill intake periods
- The percentage of subjects with  $OS_q$ ,  $OS_a$ ,  $OS_a/OS_{alp}$  and  $OS_{nlp}$  in missed pill periods
- The percentage of subjects with  $OS_{nlp}$  in all periods

A stratified McNemar test (stratification on the site, CMH option in SAS) will be used to compare the distribution of ovarian activity classification in the perfect use period to the delayed and missed pill periods (pairwise vs perfect use). The worst (meaning most risk of ovulation) ovarian activity category in the period will be used for the analyses.

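### The McNemar tests are specified as CMH stratified by site, which is not a paired test of equal proportions

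*SAP*

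**What the plan says.** Section 3.7.1 introduces the test with "Comparison between the missed pill and the delayed pill can easily be performed" and says it is "tested through a stratified McNemar test (stratification on the site, CMH option in SAS"). It then states two null hypotheses. The first is "Proportion of protected women at baseline (R-1) is equal to the proportion of protected women after schedule infringement", at Day R. The second, for the missed pill only, equates the proportions at R-1 and R+1. Section 3.7.1 also rules out the GLIMMIX procedure for the decision-making test, so this test fills that role.

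Section 3.7.2.1 states: "A stratified McNemar test (stratification on the site, CMH option in SAS) will be used to compare the distribution of cervical mucus scores". The endpoint there has three classes, although the section also says "The cut off is a cervical mucus score of 4". Section 3.7.2.2 states: "A stratified McNemar test (stratification on the site, CMH option in SAS) will be used to compare the distribution of ovarian activity classification". Ovarian status has four ranked classes, and no binary cut is given for the test.

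Elsewhere the plan is plainly paired. In the efficacy table of Section 2.4.2, the row "Absence of risk increase further to delayed intake" and the other rows for these three objectives show McNemar alone, with no stratum and no CMH. Section 2.5 sizes the study on within-woman discordance: "if the proportion of discordances between the 2 situations is 17% then the exact power is equal to 79.1"%. The only SAS code in the SAP is for the mixed model.

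**The concern.** McNemar compares two proportions measured in the same women and uses only those whose status changes. CMH gives the same statistic if every woman is a separate stratum. With site as the stratum it does something else, in one of two ways:

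- **Crossed layout** (site × first result × second result): tests whether a woman's two results are associated. This is not the hypothesis stated.
- **Stacked layout** (site × condition × response): compares the right proportions but treats a woman's two results as coming from different women.

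Two further points in the same text leave the test open. Section 3.7.1 attaches it to missed versus delayed pill, while the nulls it states compare R-1 with R or R+1. Sections 3.7.2.1 and 3.7.2.2 ask a two-category test to compare distributions over three or four classes.

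The p-values at stake are those for the subordinate primary, mucus-protection and ovarian-activity objectives. A programmer who runs plain McNemar gets valid ones; a programmer who follows the parenthesis does not.

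**Working it through.** **Inputs.** From the SAP: 45 completers, with a 14% difference at 17% discordance or a 15% difference at 18% (Section 2.5); two-sided 0.05 (Section 3.1); two sites, inferred from the wording of Section 5.2. Assumed: a 23/22 site split, and the share of women unprotected in both conditions (0, 1, 3.5, 10 or 20%), which the SAP does not give.

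**The SAP's own power.** A 14% difference with 17% discordance means (17+14)/2 = 15.5% change one way and (17-14)/2 = 1.5% the other. Enumerating all outcomes for n = 45, the exact unconditional paired test at one-sided 0.05 gives 79.10%, and 82.43% for 15%/18%. Both match the SAP, which confirms that the design is paired. Two-sided, the same test and asymptotic McNemar both give 69.5% and 73.6%. That gap is a separate matter; 69.5% is the benchmark below.

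**Formulas.** With b women losing and c women gaining protection, McNemar = (b-c)²/(b+c). In CMH with subject as stratum, each discordant woman adds ±1/2 to the numerator sum and 1/4 to the variance, and concordant women add nothing. The statistic is [(b-c)/2]² / [(b+c)/4], which is McNemar exactly. With site as stratum, CMH = [Σ(n11 - r1·c1/n)]² / Σ[r1·r2·c1·c2/(n²(n-1))], where r and c are row and column totals.

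**Worked table.** Seven women lose and one gains protection. By site (protected both, lost, gained, unprotected both): 16, 4, 0, 3 and 16, 3, 1, 2.

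- McNemar: (7-1)²/8 = 4.50, p = 0.034.
- Crossed: differences (16 - 20·16/23) + (16 - 19·17/22) = 2.087 + 1.318 = 3.405; variance 6720/11638 + 4845/10164 = 0.577 + 0.477 = 1.054; 3.405²/1.054 = 11.0, p = 0.0009.
- Stacked: differences (20-18) + (19-18) = 3; variance 2.000 + 1.674 = 3.674; 9/3.674 = 2.45, p = 0.12.

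Keeping 7 versus 1 and changing only the number unprotected in both leaves McNemar at 0.034:

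| Unprotected in both | Crossed p | Stacked p |
|---|---|---|
| 0 | 0.69 | 0.028 |
| 2 | 0.035 | 0.066 |
| 5 | 0.0009 | 0.12 |
| 9 | 0.00006 | 0.17 |

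With four women changing each way (15, 2, 2, 4 and 15, 2, 2, 3), McNemar is 0, p = 1.00, while the crossed layout gives 11.5, p = 0.0007.

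**Rejection rates.** Exact enumeration, uncorrected chi-square, two-sided 0.05. The null has 8.5% discordant each way; the alternative has 15.5%/1.5%. McNemar rejects in 4.5% and 69.5% throughout. Trials where the crossed statistic cannot be computed count as no rejection.

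| Share unprotected in both | Null: crossed | Null: stacked | Alternative: crossed | Alternative: stacked |
|---|---|---|---|---|
| 0% | 0.0% | 5.9% | 0.0% | 72.5% |
| 1% | 6.7% | 4.9% | 15.0% | 67.5% |
| 3.5% | 29.8% | 3.1% | 48.5% | 56.5% |
| 10% | 77.1% | 1.0% | 89.8% | 36.1% |
| 20% | 97.0% | 0.3% | 99.3% | 21.1% |

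A 32/13 site split at the 10% share hardly changes this: null 77.2% and 1.0%, alternative 89.7% and 36.0%. Under the alternative, the crossed statistic cannot be computed in 52, 33, 10, 0.4 and 0% of trials as the share rises.

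**The case against.** The strongest reply is that the SAP names McNemar and never says site is the only stratum. Subjects are nested in site, so the words could be read as CMH on subjects within sites, which is McNemar; the fault would then be missing detail. But that reading needs a subject stratum that appears nowhere in the SAP, and once subject is the stratum, site has no further role. The instruction as written does not lead there.

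Several other points stand:

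- The crossed layout is the less likely reading. It cannot be computed if every woman is protected at R-1, so the error would then show. Its high rejection rates should not set the weight of the point.
- The stacked layout is the more realistic slip. At 0 to 1% unprotected in both it is practically McNemar, and above that it errs conservatively. Section 2.5 expects most changes to go from protection to loss, which may suggest a low share for R-1 versus R. The worst-score-per-period analyses could have a higher one, but the SAP gives no figure for either.
- The two numbered nulls in Section 3.7.1 do fix their time points. What stays open is whether missed versus delayed pill is also tested. Sections 3.7.2.1 and 3.7.2.2 fix their pairs, each infringement period against perfect use.
- The study is exploratory.

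**Conclusion.** The concern holds. The method in the parenthesis is not a valid paired test of the stated nulls under either layout, and it conflicts with the McNemar entries in Section 2.4.2 and the paired sizing in Section 2.5. The size depends on the unstated share unprotected in both conditions. For the stacked layout, power at 14%/17% runs from 72.5% at a 0% share to 21.1% at 20%, against 69.5% for McNemar. The crossed layout answers a different question at any share. These figures rest on 45 women, two sites and the assumed shares. The mismatch between a binary test and multi-class endpoints is a second fault, clearest in Section 3.7.2.2, where no cut is stated. The mixed-model primary test and all descriptive proportions are untouched. This should be corrected before the tests are programmed.

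**What to change.** In Sections 3.7.1, 3.7.2.1 and 3.7.2.2, replace the site-and-CMH parenthesis with either McNemar on within-woman pairs (PROC FREQ, AGREE option) or CMH with subject as the stratum, and add the code.

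- **Section 3.7.1:** list the pairs: R-1 versus R for each infringement type, R-1 versus R+1 for the missed pill, and missed versus delayed pill if that is intended.
- **Section 3.7.2.1:** say that McNemar uses the cut-off already stated (≤4 versus >4), or name a paired test for three classes: Bowker, Stuart-Maxwell or subject-stratified CMH row mean scores.
- **Section 3.7.2.2:** name such a multi-category paired test, or state a binary cut, for example the OSnlp endpoint already listed.

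The cost is SAP wording and about one line of SAS per analysis. No data collection changes.

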### 3.7.2 Secondary Efficacy Analyses

#### 3.7.2.1 Cervical mucus protection in each type of treatment period

The aim of this secondary objective is to assess the level of cervical mucus protection during reported perfect use, during a treatment period with a delayed pill intake of 6 hours and during a treatment period with a missed pill of norgestrel 75 mcg. The FASM population will be used for the analysis and a sensitivity analysis will be done using ITT and PP.

The time frames are:

- reported perfect use: all the visits of the period 1
- delayed pill intake: all the visits of the period 2 for Arm A and all the visits of period 3 for Arm B.
- missed pill: all the visits of the period 2 for Arm B and all the visits of period 3 for Arm A.

The assessment criterion is the cervical mucus score. The cut off is a cervical mucus score of 4. There is conception protection by cervical mucus if the cervical mucus score is  $\leq 4$ .

The endpoints are:

- The percentage of subjects with cervical mucus score  $\leq 4$ , between 5 and 8, and  $\geq 9$  in reported perfect use period
- The percentage of subjects with cervical mucus score  $\leq 4$ , between 5 and 8, and  $\geq 9$  in delayed pill intake periods
- The percentage of subjects with cervical mucus score  $\leq 4$ , between 5 and 8, and  $\geq 9$  in missed pill periods
- The percentage of subjects with cervical mucus score  $\leq 4$  in all periods

If the cervical mucus was too thick to be collected (and thus a cervical mucus score could not be obtained) the analysis will consider the sample to have good contraception protection and have a cervical mucus score  $\leq 4$ . Otherwise if the cervical mucus score is missing the subject will not be included in the analysis. A period must have at least 7 cervical mucus assessment to be included in the summaries. A stratified McNemar test (stratification on the site, CMH option in SAS) will be used to compare the distribution of cervical mucus scores in the perfect use period to the delayed and missed pill periods (pairwise vs perfect use).

The worst (meaning highest) cervical mucus score in the period will be used for the analyses.

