### 2.2 Objectives

The primary objectives of the study are:

- to determine the effect of a delayed intake of 6 hours or of a missed pill on cervical mucus score compared to cervical mucus score during reported perfect daily use of norgestrel 75 mcg
- to estimate the duration of the protective effect of cervical mucus after last pill intake of norgestrel 75 mcg during reported perfect use (The protective effect of cervical mucus is considered as present when the score is below or equal 4.)

---

 defined as the day before the delayed intake or the missed pill

The secondary objectives of the study are:

[figure not shown]
- to evaluate and compare the percentage of subjects with a protective cervical mucus score during reported perfect daily use of norgestrel 75 mcg, during a treatment period with a delayed intake of 6 hours and during a treatment period with a missed pill of norgestrel 75 mcg.
- to evaluate and compare the ovarian activity during reported perfect daily use, during a treatment period with a delayed intake of 6 hours and during a treatment period with a missed pill of norgestrel 75 mcg.
- to assess if a combination of cervical mucus score and ovarian status can be considered as a measure of protection from conception during reported perfect daily use, during a treatment period with a delayed intake of 6 hours and during a treatment period with a missed pill of norgestrel 75 mcg.
- to determine levonorgestrel pharmacokinetics after a single dose of norgestrel 75 mcg, at steady state, after a delayed intake and after a missed pill.
- to assess the safety of norgestrel 75 mcg taken daily for 12 weeks.

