### 2.3 Design

This is an exploratory, prospective, multi-center, randomized, cross-over study to assess the effect of norgestrel 75 mcg on cervical mucus and ovarian activity during reported perfect daily use and after a delayed intake of 6 hours and after a missed pill.

Women of reproductive age (18-35 years old inclusive) who meet eligibility requirements will be recruited for this study. This study has a screening period of up to 1 month to demonstrate ovulatory status prior to enrollment followed by three 28-day treatment periods (approximately 3 months) and a possible follow-up of 12 days if ovarian activity shows a follicle  $\geq 15$  mm is observed at the end of period 3 and an end of study (EOS) visit within 5 days. During the treatment period 2 the subjects will be randomized into two arms: Arm A will have a delayed pill intake of 6 hours on D42 ( $\pm 3$  days) and Arm B will have a missed pill (24-hour delayed pill intake on D42 ( $\pm 3$  days)). In the next treatment period, these subjects will cross-over meaning Arm A will have a missed pill (24-hour delayed pill intake) on D70 ( $\pm 3$  days) and Arm B will have a delayed pill intake of 6 hours on D70 ( $\pm 3$  days) (see Figure 1 below).

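### The tested mucus contrast in SAP 3.7.2.1 takes the worst score over a whole 28-day period, of which about 13 days precede the infringement, so it cannot be attributed to the delayed or missed pill

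*SAP*

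**What the plan says.** SAP 2.3 plans a screening phase "followed by three 28-day treatment periods". The infringement falls in the middle of periods 2 and 3. For example, "Arm A will have a delayed pill intake of 6 hours on D42" (±3 days), with the crossover infringement on D70 (±3 days). The schedule in Appendix 5.1 gives period 2 as D29 to D56 and period 3 as D57 to D84.

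SAP 3.7.2.1 sets three time frames for the secondary mucus analysis. Perfect use is the whole of period 1. The frame for the late pill is given as "delayed pill intake: all the visits of the period 2 for Arm A and all the visits of period 3 for Arm B". The third frame mirrors this one with the arms exchanged, so it too spans an entire period.

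Within each frame one value per woman is kept: "The worst (meaning highest) cervical mucus score in the period will be used for the analyses". A period needs at least 7 assessments. Each infringement period is compared with period 1 by a site-stratified McNemar test.

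SAP 3.7.2.2 uses the same windows for ovarian status ("missed pill period: all the visits of the period 2 for Arm B and all the visits of period 3 for Arm A"), again with the worst category and the same test.

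For the primary objectives only, a footnote in 2.2 describes perfect use differently: "defined as the day before the delayed intake or the missed pill". A second footnote equates perfect use with treatment period 1 for the secondary objectives.

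**The concern.** The windows are named after an event that happens about halfway through them. The summary is a maximum, so one score of 5 or more at, say, D33 fixes the woman's category for the delayed-pill or missed-pill period even if every score from the infringement onward is 4 or less. No rule in the SAP removes such a score. The very early ovulation clause in 3.4 is optional, concerns ovulation, and acts on whole cycles.

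What is at stake is how the tested contrast is read. Readers will take a significant difference from period 1 as an effect of the late or missed pill, although part of what was counted came before it.

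**Working it through.** The SAP gives no figure for this point and no background rate of high scores. What follows is calendar arithmetic plus an illustration under stated assumptions. The one number borrowed from the plan is the 14% difference in SAP 2.5.

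**1. Days before the infringement (day R).** Days before R = R − first day of period.
- Period 2: 42 − 29 = 13. Period 3: 70 − 57 = 13.
- With R three days earlier: 39 − 29 = 10. Three days later: 45 − 29 = 16.
- Share of the period: 13/28 = 46% (10/28 = 36% to 16/28 = 57%).
- Days from R to the end: 28 − 13 = 15 (12 to 18).

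**2. Mucus visits.** Visits are twice weekly outside the three infringement days (Appendix 5.1).
- Before R: D29 to D40 is 12 days; 12 × 2/7 = 3.4; adding the R−1 visit gives 4 to 5.
- From R on: R, R+1, and D44 to D56 (13 days; 13 × 2/7 = 3.7), about 6.
- Whole period: about 10 to 11. Period 1: 28 × 2/7 = 8.

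Extra visits for a growing follicle are ignored.

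**3. Women fixed as unprotected before R.** Let q be the assumed chance of a score above 4 at a visit under daily intake, with visits independent. P(at least one of 5) = 1 − (1 − q)^5.

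| q | At least one high score before R |
|---|---|
| 0.5% | 2.5% |
| 1% | 4.9% |
| 2% | 9.6% |
| 5% | 22.6% |

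With 4 earlier visits the ends of the range are 1 − 0.995^4 = 2.0% and 1 − 0.95^4 = 18.5%. Correlation within women lowers the figures: a beta-binomial model with intraclass correlation 0.1 and 5 visits gives 8.0% at q = 2% and 19.1% at q = 5%.

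**4. Share of unprotected women who are so only because of visits before R.** Assume 5 visits before R, then R and R+1, then 4 later visits, and a true added loss of 14% at R/R+1.
- a = 1 − (1 − q)^5
- b = 0.14 + 0.86 × [1 − (1 − q)^2]
- c = 1 − (1 − q)^4
- share = a(1 − b)(1 − c) / [1 − (1 − a)(1 − b)(1 − c)]

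For q = 0.5%, 1%, 2% and 5% the share is 11.1%, 17.3%, 23.5% and 28.0%. If the window starts at R it is zero by construction.

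**5. Visit counts, with no infringement effect at all.** Proportion unprotected = 1 − (1 − q)^(visits).

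| q | Infringement period, 11 visits | Period 1, 8 visits |
|---|---|---|
| 0.5% | 5.4% | 3.9% |
| 1% | 10.5% | 7.7% |
| 2% | 19.9% | 14.9% |
| 5% | 43.1% | 33.7% |

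This gap comes from the extra consecutive visits, not from the days before R as such. Starting the window at R does not remove it. About 6 visits against about 4 in D14 to D28 (15 × 2/7 = 4.3) gives, at q = 5%, 1 − 0.95^6 = 26.5% against 1 − 0.95^4 = 18.5%. The ratio is 1.43, compared with 43.1/33.7 = 1.28 for whole periods. Using the regular visits plus only one of R and R+1 gives 3.7 + 1 = 4.7 expected visits against 4.3, which is close to balance.

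**6. Power.** In the same model with 45 women and a two-sided unstratified McNemar z-test, the whole-period test (11 against 8 visits) has power 59.6%, 50.2%, 44.3% and 39.4% for the four values of q. A window from R with 6 visits on each side has 59.3%, 45.2%, 31.9% and 18.5%. Some of the whole-period power is the visit-count artefact of step 5, but there is no power gain to claim for the shorter window.

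**The case against.** The strongest defence is that the window does what the secondary objective asks. That objective concerns protection across a treatment period that contains a delayed or missed pill, and the SAP declares period 1 as perfect use for it. A reader might infer that the SAP contradicts itself by using R−1 as perfect use in one place and as infringement time in another. The documents do not support that: the two footnotes in 2.2 give separate definitions for the primary and secondary objectives.

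Period 1 is also a whole-period maximum, so background high scores enter both sides of the paired comparison. A reader might take the percentages in step 3 as the bias in the contrast. They are not: they describe one side only and rest on an assumed rate.

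The direct question is answered elsewhere. The primary model and the subordinate primary responses use only R−1, R and R+1, and the transient and prolonged risk categories require a score of 4 or less at R−1. The study is declared exploratory.

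All of this stands, and it limits the severity. It does not justify testing the whole-period maximum as though it isolated the infringement. The adjudication committee can exclude cycles but is given no rule for high mucus scores before R, and the per-protocol set addresses early ovulation and compliance, not this.

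**Conclusion.** The point holds for the secondary mucus contrast in 3.7.2.1 and, through the shared window, for ovarian status in 3.7.2.2. About 13 of 28 days (10 to 16) precede the infringement, and a high score in them alone can set a woman's category. At an assumed 0.5% to 5% per visit, with five independent earlier visits, this touches 2.5% to 23% of women. The true rate is not in the SAP.

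It is tempting to conclude that days before the infringement decide the study's result. That is certain only for an individual woman's category. How far the group test moves is unknown, and the primary and subordinate primary analyses are untouched. The issue is attribution and interpretation, not lost power. It should be fixed, but it does not undermine the trial's main analysis.

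**What to change.** **Mucus (3.7.2.1, with 2.4.2 to match).** Keep the whole-period worst score as a descriptive row, since it matches the objective. Base the McNemar contrast on the worst score from the R visit to the end of the period, against the matching cycle days of period 1 (about D14 to D28). Add a version balanced for visit count, for example the regular twice-weekly visits plus only one of R and R+1.

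**Assessment minimum.** About 4 to 6 visits remain in the shorter window, so 7 cannot be kept. Set a lower number in advance. As a guide, 7 of about 10 is 70%, and 70% of 5 is 3.5, so 3 or 4.

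**Ovarian status (3.7.2.2).** Do not cut at R. The status in Appendix 5.4 depends on a sequence of ultrasound and progesterone findings, so a cut would break the sequence and could still charge an ovulation just before R to the infringement. Keep the committee's whole-cycle classification. Report ovulations whose postovulatory image precedes R on a separate line, not attributed to the infringement.

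**Period 3.** Visits before R in period 3 follow the first infringement. Do not pool them as perfect use without a carry-over caveat.

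**Cost.** SAP wording and one derived visit-window flag on data already planned. The downside is fewer assessments per window and no gain in power. Settle it before any data are analysed, so that the window is not chosen after the fact.
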